## 6.2. Special Handling for COVID-19 Disruptions

In some cases, study visits will have to be delayed/not performed as a result of COVID-19 disruptions (e.g., sites were closed, or subjects were under stay-at-home orders). Where possible, study sites may collect post-baseline data from subjects remotely by telemedicine, traditional mail, and/or email; this will be clearly documented in the source. If possible, sites should adhere to the protocol visit window for remote data collection.

Investigator assessments and subject questionnaires normally completed directly during on-site visits should be completed on the appropriate paper source documents. The following assessments/questionnaires are approved to be collected via telemedicine/remote:

- WI-NRS
- DLQI/CDLQI
- Scalpdex
- C-SSRS
- PHQ-8/PHQ-A/CDI-2
- Subject Local Tolerability

The following assessments cannot be completed via telemedicine/remote:

AD-ST-33.06 Effective date: 12-Nov-2020

- IGA
- BSA
- Investigator Local Tolerability
- Overall Assessment of Erythema
- Overall Assessment of Scaling
- Pigmentation Assessment
- Subject Weight

Study visits and procedures must be followed per protocol whenever possible. Any specific changes in study conduct that deviate from the protocol should be communicated to the institutional review board and Sponsor. All protocol deviations which occurred as a result of COVID-19 disruptions (e.g., visits out of window, missed assessments, etc.) will be differentiated from other protocol deviations.

Subjects who were affected by COVID-19 disruptions by either missing their Week 8 visit or being discontinued before having a Week 8 visit due to COVID-19 related disruptions will be excluded from the mITT population, as described in [Section 5](#).

## **7. STUDY PATIENTS/SUBJECTS AND DEMOGRAPHICS**

### **7.1. Disposition of Patients/Subjects and Withdrawals**

Disposition will include tabulations of the number of the screened subjects, the number of the subjects who failed screen, the number of subjects randomized into each treatment group, the number of subjects who received treatment, subjects completing the study, the reasons for discontinuation from the study overall and due to COVID-19 disruption, and the number of subjects in each analysis population. Disposition will be summarized for all subjects who were entered into database by treatment group and overall.

A listing of subject's disposition will be provided. The reasons for screen failures will be listed.

### **7.2. Protocol Deviations**

Important deviations will be identified based on a blinded review at the end of the study performed by the study team. The number of subjects with important protocol deviations will be summarized in categories by treatment group and overall, for subjects in the ITT population.

A listing of all protocol deviations will also be provided.

In addition, all the protocol deviations associated with COVID-19 will be summarized by deviation category and listed as described above.

### **7.3. Demographics and Baseline Characteristics**

Summary statistics for age, age groups (9-17 years, 18-64 years and  $\geq$  65 years old), gender (including child-bearing potential), race, ethnicity, height, weight, BMI, baseline disease characteristics (IGA, Overall Assessment of Erythema, Overall Assessment of Scaling, Scalpdex, average weekly WI-NRS, daily WI-NRS, DLQI, CDLQI), Fitzpatrick skin type, percent BSA affected by disease, and body parts involved will be presented by treatment group and overall.

A summary of seborrheic treatment history, including history of response, intolerance, or contraindication to topical corticosteroids and/or topical antifungals, and off-label use of topical calcineurin inhibitors will be provided.

For the continuous variables, the number of non-missing values and the mean, standard deviation, median, Q1, Q3, minimum, and maximum will be tabulated.

For the categorical variables, the counts and proportions of each value will be tabulated.

For ordinal variables such as the IGA, Overall Assessment of Erythema, Overall Assessment of Scaling, and daily WI-NRS, summary statistics including the mean, median, Q1, Q3, and range of the ordinal variable will be presented. Frequency counts of each level of the categorized variables will also be presented.

These analyses will be conducted for the ITT and Safety populations separately (if these two populations include different sets of subjects).

A listing of all demographics, analysis population flag, reasons not included in the efficacy analysis will be provided.

### **7.4. Exposure and Compliance**

The number of expected IP applications will be summarized by treatment group.

The number of IP applications by each subject based on diary data will be summarized by treatment group using descriptive statistics appropriate for continuous variables.

The amount of IP used by each subject based on can weight will be summarized descriptively by treatment group using continuous methods.

The number of days on IP will be summarized descriptively by treatment group.

A subject will be considered compliant with the dosing regimen if the subject applies at least 80% of the expected applications during the IP application period and does not miss more than 3 consecutive doses.

Investigational product application compliance will be calculated based on number of applications divided by the expected number of IP applications. Compliance will be summarized descriptively by treatment group using the following categories:

- 100%
- $\geq 80\% - \leq 100\%$
- < 80%

A listing of drug exposure will also be provided.

## 8. EFFICACY ANALYSIS

Efficacy analysis will be based on ITT population unless specified otherwise. The randomized treatment arm and strata will be used in the efficacy analysis.

The efficacy analyses that include the stratification factors (pooled sites, IGA strata (“3” (moderate) and “4” (severe)) will use the data as collected in the interactive web response system (IWRS). A table of randomized strata vs. actual strata will be provided if there is any mis-randomization.

### 8.1. Primary Efficacy Analysis

The order of testing for the primary and secondary endpoints is discussed in [Section 6.1.3](#). Other secondary endpoints are not included in the testing strategy.

In general, for efficacy analysis, the CMH test is performed on both imputed and observed data. Numerical summaries, categorical frequencies of each severity group are summarized using observed data only. Analysis of imputation results are summarized for ITT population only unless specified otherwise. In rare cases, the odds ratio is not estimable due to zero event in one of the categories, the odds ratio and associated p-value will not be reported. If a non-estimable odds ratio and associated p-value occur as part of the multiple testing strategy, the p-value to be used in the testing strategy will be based on a test of a difference in proportions.

#### 8.1.1. IGA Success

The IGA is an ordinal scale with five severity grades which is reported only in integers. [Table 3](#) illustrates the description of each severity grade.

**Table 4:** IGA

Score	Description
0	Clear: No erythema, no scaling (hypo-hyperpigmentation can be present)
1	Almost Clear: Slight erythema and/or trace (barely perceptible) amounts of scaling
2	Mild: Pink to red color and/or slight scaling
3	Moderate: Distinct erythema (redness) and/or clearly visible scaling

4

**Severe:** Severe erythema (intense, fiery red) and/or severe scaling (coarse, thick scales with flaking onto clothes or skin)

The primary efficacy endpoint is success in IGA of disease severity, defined as IGA score of “Clear” or “Almost Clear” plus at least 2-point improvement from baseline at Week 8. The definition is the same as IGA score of “Clear” or “Almost Clear” given all subjects are enrolled in this study with moderate or severe IGA.

The primary statistical comparison will be as follows:

- Roflumilast foam 0.3% versus Vehicle foam

The primary estimand is based on feedback from FDA received after database lock and unblinding and is described by the following attributes:

Population: Seborrheic Dermatitis

Intercurrent events: In the course of the 8-week randomized treatment period, subjects may be exposed to possible known or unknown intercurrent events that could possibly impact the estimates of the estimand, such as treatment discontinuation due to a specific adverse effect or perhaps a lack of effect. A composite strategy will be implemented that handles subjects who discontinue due to lack of efficacy or adverse event as missing not at random, differently than all other subjects. The “Treatment Policy Strategy” has been adopted for handling all other known or unknown intercurrent events in this study other than discontinuation due to lack of efficacy or adverse event. Subjects who discontinue due to lack of efficacy or adverse event will be treated as non-responders at all analysis visits that occurred or would have occurred on or after the date of last dose of treatment application.

The original primary estimand has been left unchanged, but re-labeled as a supplemental estimand and will handle all intercurrent events using a “Treatment Policy Strategy”, including discontinuation due to lack of efficacy or adverse event. Multiple imputation procedures are described in Section 6.1.4.1.2.

Population-level summary: ratio of the odds of achieving IGA success after 8 weeks of using ARQ-151 (roflumilast foam 0.3%), relative to the odds of success after 8 weeks using a matching vehicle foam.

The supportive population-level summary: the proportion difference between ARQ-151 foam 0.3% and vehicle groups will be provided for the patients who achieve IGA success at week 8.

Rationale for the estimands: Odds ratio of achieving IGA success for ARQ-151 (roflumilast foam 0.3%) relative to vehicle after 8 weeks and the proportion difference of achieving IGA success will be evaluated regardless of the occurrence of any such intercurrent event. The odds ratio will be obtained from CMH test stratified by the randomization factors (by baseline IGA

score and by pooled study site). The strata-adjusted proportion difference will be obtained from CMH method based on stratification factors of baseline IGA and study sites.

Statistical significance will be concluded as described in section 6.1.3. 99% CIs for the odds ratios and for the stratified proportion difference between treatment arm will be provided. Additionally, the 99% CI for proportion of subjects who achieved IGA successes in each treatment group will be presented. 95% CIs for the odds ratios and the stratified proportion difference in each treatment arm are provided as well. Both 99% CI & 95% CI will be presented for all the efficacy endpoints. For the primary analysis, missing IGA scores will be imputed using multiple imputation as described in [Section 6.1.4](#). These imputations will result in a total of 150 complete analysis datasets.

The CMH analyses will be performed separately for each of the complete analysis data sets, and the results will be combined into one multiple imputation inference (stratified proportion differences and associated CI, odds ratio and associated CI and p-value). The proportion of subjects who achieved IGA success and associated CI, using an extension of Wilson's method proposed by [Lott and Reiter](#), will be reported using multiple imputation as well.

IGA numeric data and change from baseline will be summarized using descriptive summaries (mean, median, inter quartile range) by treatment group and study visit using observed data.

### **8.1.2. Hypothesis Testing**

Primary hypothesis testing on the odds ratio: The null hypothesis is that the IGA Success does not differ between roflumilast foam 0.3% and matching vehicle foam. The alternative hypothesis is that the IGA Success does differ between roflumilast foam 0.3% and matching vehicle foam.

Null Hypothesis ( $H_0$ ):  $P_R Q_V / P_V Q_R = 1.0$ ,

Alternative Hypothesis ( $H_A$ ):  $P_R Q_V / P_V Q_R \neq 1.0$ , where

$P_R$  = the proportion of IGA Success in roflumilast foam 0.3%

$P_V$  = the proportion of IGA Success in matching vehicle foam

$Q_R = 1 - P_R$

$Q_V = 1 - P_V$ .

### **8.1.3. Sensitivity and Supplemental Analyses of the Primary Efficacy Endpoint**

The following sensitivity and supplemental analyses will be performed for primary efficacy endpoint, based on the CMH test as described in [Section 8.1.1](#):

- The primary efficacy endpoint analysis repeated on subjects in the PP population using observed data.
- The primary efficacy endpoint analysis repeated on subjects in the mITT population on

MI imputed data.

- The primary efficacy endpoint analysis repeated on subjects in the ITT population using observed data.
- The primary efficacy endpoint analysis repeated on subjects in the ITT population using non-responder imputation in which the post baseline missing will be considered as non-responder (no IGA success).
- The primary efficacy endpoint analysis repeated on subjects in the ITT population on MI imputed data using CMH model without site stratification.
- A tipping point analysis will be performed as described in [Section 6.1.4.2](#)

#### **8.1.4. Impact of Site on the Primary Efficacy Endpoint**

The following supportive analysis will be performed to investigate the impact of site on the primary endpoints.

- To assess the impact of site on the primary analysis endpoint, the proportion of subjects achieving IGA success and 99% CI within each site will be plotted by treatment groups. No p-values will be provided.
- An additional analysis to examine the impact of study site will examine the changes in p-values that occur after removal of subjects from a site. First, remove subjects from one site from the MI datasets, recalculate the combined CMH p-value as described for the primary analysis, and repeat removing a different site for each iteration. The p-values from the iterations will be plotted by the site removed.

### **8.2. Secondary Efficacy Analysis**

All secondary efficacy analyses will be performed using the ITT unless specified otherwise. The sensitivity analysis will be performed in a similar fashion as those in the primary efficacy endpoint as described in [Section 8.1.3](#). See the list of sensitivity analysis for secondary endpoints in table 6).

The statistical comparison will be as follows:

- Roflumilast foam 0.3% versus Vehicle foam

#### **8.2.1. Investigator Global Assessment (IGA)**

Secondary efficacy endpoints in the multiple testing scheme related to the IGA include the following:

- IGA Success at Week 4
- IGA Success at Week 2

- Achievement of an IGA score of ‘clear’ at Week 8.

The above analysis will be performed on subjects in the ITT, for imputed and observed data, unless otherwise specified using the similar CMH test and the stratified proportion difference as described in [Sections 8.1.1.](#) and [8.1.3.](#) The sensitivity analysis for IGA endpoints (IGA success at Week 2, Week 4 and IGA score of 0 at Week 8) will be provided in a similar fashion as those in the primary endpoint as summarized in Table 6.

### **8.2.2. Worst Itch – Numeric Rating Scale (WI-NRS) Pruritus Score**

Secondary efficacy endpoints related to WI-NRS pruritus score, which are all based on average weekly WI-NRS unless specified otherwise, include the following:

- In subjects with baseline WI-NRS pruritus score of  $\geq 4$ , achievement of at least 4-point improvement from baseline in WI-NRS pruritus score at Week 8 (“WI-NRS Success at Week 8”).
- WI-NRS Success at Week 4.
- WI-NRS Success at Week 2.

The following analyses are performed for WI-NRS:

- In subjects with a baseline WI-NRS score  $\geq 4$ , WI-NRS success endpoint (at Week 2, at Week 4 and at Week 8) will be analyzed in a similar fashion as those for the primary endpoint.
- The primary efficacy endpoint analysis repeated on subjects in the PRU4-ITT population using non-responder imputation in which the post baseline missing will be considered as non-responder (no WI-NRS success).

### **8.2.3. Other Efficacy Endpoints**

Other efficacy endpoints related to average weekly WI-NRS pruritus score:

- Change and percent change from baseline in average weekly WI-NRS pruritus score at Weeks 2, 4, and 8 will be performed using descriptive summaries (mean, median, inter quartile range) by treatment group and study visit using observed values.
- Change and percent change from baseline in average weekly WI-NRS at Weeks 2, 4, and 8 will be analyzed using an analysis of covariance (ANCOVA) model with terms for treatment, pooled study site, and baseline IGA as covariate. The observed value will be used. Statistical comparisons between the treatment groups will be obtained using contrasts. The LS Means, standard errors, 95% and 99% confidence intervals, and p-values will be presented at each visit. These analyses will be performed on the ITT populations. The p-values are nominal and there is no formal inferential testing on other efficacy endpoints.

Other efficacy endpoints related to daily WI-NRS pruritus score:

- Change and percent change from baseline in daily WI-NRS score will be provided by treatment groups along with plots of daily WI-NRS (mean and SD of observed value and percent change from baseline).
- Similar ANCOVA model will be performed for change and percent change from baseline daily WI-NRS every day in the first week, at Weeks 2, 4 and 8 using observed data.

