### **2.2.1.3. Other Secondary Efficacy Endpoint(s)**

Other secondary efficacy endpoints of this study include the following:

- Change and percent change in Scalpdex total score from baseline at Weeks 2, 4, and 8.
- Achievement of an Overall Assessment of Erythema (0-3 scale) score of 0 at Weeks 2, and 4.
- Achievement of an Overall Assessment of Scaling (0-3 scale) score of 0 at Weeks 2, and 4.
- Change and percent change from baseline in Dermatology Life Quality Index (DLQI), Children’s DLQI (CDLQI) at Weeks 2, 4, and 8.
- Change and percent change from baseline in body surface area (BSA) affected at Weeks 2, 4, and 8.
- Change and percent change from baseline in Overall Assessment of Erythema score at Weeks 2, 4, and 8.
- Change and percent change from baseline in Overall Assessment of Scaling score at Weeks 2, 4, and 8.
- Achievement of an IGA score of ‘clear’ at Week 4.
- Achievement of an IGA score of ‘clear’ at Week 2.
- Achievement of daily WI-NRS score of 0 or 1.
- Change and percent change from average weekly baseline in WI-NRS

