**Table 3: Erythema Grades**

Score	Description
0	None: No evidence of erythema
1	Mild: Barely perceptible erythema which is faint or patchy
2	Moderate: Distinct erythema,
3	Severe: Intense (fiery red) erythema

Secondary endpoint that is included in the multiple testing scheme is

- Achievement of an Overall Assessment of Erythema (0-3 scale) score of 0 at Week 8

The analysis of Erythema of 0 is performed similar to the primary endpoint including the sensitivity analysis on both imputed and observed data.

Analysis of efficacy endpoints related to erythema score will be performed using ITT population using observed value:

- The number and percentage of subjects in each category will be summarized by treatment and study visit descriptively
- An ANCOVA model similar to what is defined in [Section 8.2.3](#) will be used for analysis of the change and percent change from Erythema baseline.

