**Table 4: Scaling Grades**

Score	Description
0	None: No scaling evident on lesions
1	Mild: Barely detectable, scattered, small flaking scales
2	Moderate: Scales clearly visible and prominent
3	Severe: Coarse, thick scales, with flaking into clothes or skin

The analysis of Scaling will be performed similar to those of erythema score as indicated in [Section 8.2.3](#).

Separate listings of IGA, average weekly WI-NRS, daily WI-NRS score, Overall assessment of Erythema, and overall assessment of scale score will be provided along with IGA success, and WI-NRS success flag.

Table 6: Summary of Primary and Secondary Efficacy Analyses

Efficacy Endpoint	Primary Analysis	Sensitivity or Supplemental Analysis
Primary		
IGA Success (IGA score of '0' or '1' plus at least 2-point improvement from baseline) at week 8	ITT, multiple imputation (CMH)	#1 PP, observed data (CMH) #2 mITT, multiple imputation (CMH) #3 ITT, observed data (CMH) #4 ITT, non-responder imputation (CMH) #5 ITT, Tipping point #6 ITT based on different site pooling strategy #7 ITT without site stratification
Secondary		

Family 1 ( $\alpha=0.0033$ ): Average weekly WI- NRS Success (achievement of at least a 4-point improvement) at Weeks 2, 4, 8	PRU4-ITT population, multiple imputation (CMH)	#1 PRU4-ITT, observed data (CMH) #2 PRU4-ITT, non-responder imputation (CMH)
Family 2 ( $\alpha=0.0067$ ): IGA Success at weeks 4	ITT, multiple imputation (CMH, odds ratio)	#1 ITT, observed data (CMH) #2 ITT, non-responder imputation (CMH)
Family 2 ( $\alpha=0.0067$ ): Scaling score of '0' at weeks 8	ITT, multiple imputation (CMH, odds ratio)	#1 ITT, observed data (CMH) #2 ITT, non-responder imputation (CMH)
Family 2 ( $\alpha=0.0067$ ): Erythema Score of '0' at Week 8	ITT, multiple imputation (CMH, odds ratio)	#1 ITT, observed data (CMH) #2 ITT, non-responder imputation (CMH)
Family 2 ( $\alpha=0.0067$ ): IGA score of '0' at Week 8	ITT, multiple imputation (CMH)	#1 ITT, observed data (CMH) #2 ITT, non-responder imputation (CMH)
Family 2 ( $\alpha=0.0067$ ): IGA Success at Week 2	ITT, multiple imputation (CMH)	#1 ITT, observed data (CMH) #2 ITT, non-responder imputation (CMH)

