### 8.3. Other Efficacy Analysis

Other secondary efficacy analysis will be performed for subjects belonging to ITT population on the observed data.

The other secondary efficacy endpoints include:

- Change and percent change in Scalpdex total score from baseline at Weeks 2, 4, and 8.
- Achievement of an Overall Assessment of Erythema (0-3 scale) score of 0 at Weeks 2, and 4.
- Achievement of an Overall Assessment of Scaling (0-3 scale) score of 0 at Weeks 2, and 4.

- Change and percent change from baseline in DLQI/CDLQI at Weeks 2, 4, and 8.
- Change and percent change from baseline in BSA affected at Weeks 2, 4, and 8.
- Change and percent change from baseline in Overall Assessment of Erythema at Weeks 2, 4, and 8.
- Change and percent change from baseline in Overall Assessment of Scaling at Weeks 2, 4, and 8.
- Achievement of an IGA score of ‘clear’ at Week 4.
- Achievement of an IGA score of ‘clear’ at Week 2.
- Achievement of daily WI-NRS score of 0 or 1 at Weeks 2, 4, 8.
- Change and percent change in WI-NRS from average weekly baseline score.

All the categorical analyses involving achievement of Erythema, Scaling, IGA, WI-NRS are summarized using CMH and proportion difference stratified by pooled site and baseline IGA and presented by study visit.

Continuous endpoints including change and percent change from baseline in average weekly WI-NRS, % BSA, Scalpdex, DLQI/CDLQI, Erythema, Scaling at Week 2, Week 4 and Week 8 will be analyzed using an analysis of covariance (ANCOVA) with the factors of treatment, pooled study site, baseline IGA score, and baseline of the variable under analysis. Similar analysis will be performed for daily WI-NRS every day in the first week and at Week 2, Week 4 and Week 8. Statistical comparisons between the treatment groups will be obtained using contrasts. The LS Means, standard errors, 95% and 99% confidence intervals, and p-values will be presented at each visit. These analyses will be performed on the ITT populations.

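### SAP 8.2.3 and 8.3 give different ANCOVA covariate lists for change in average weekly WI-NRS, without and with its own baseline, and the public documents do not say which applies

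*SAP*

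**What the plan says.** SAP 2.2.1.3 includes "Change and percent change from average weekly baseline in WI-NRS" among the other secondary endpoints. The analysis is then described twice.

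- **SAP 8.2.3** uses an "analysis of covariance (ANCOVA) model with terms for treatment, pooled study site, and baseline IGA as covariate", on observed values in the ITT population, at Weeks 2, 4 and 8.
- **SAP 8.3** opens with "Other secondary efficacy analysis will be performed for subjects belonging to ITT population on the observed data". It names change and percent change in average weekly WI-NRS among its continuous endpoints and gives an ANCOVA "with the factors of treatment, pooled study site, baseline IGA score, and baseline of the variable under analysis".

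Both sections promise LS means, standard errors, 95% and 99% confidence intervals and p-values.

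Other endpoints are tied to one or both models by the word *similar*:

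- **Daily WI-NRS:** 8.2.3 says "Similar ANCOVA model will be performed for change and percent change from baseline daily WI-NRS every day in the first week"; 8.3 says "Similar analysis will be performed for daily WI-NRS every day in the first week and at Week 2, Week 4 and Week 8".
- **Erythema:** 8.2.4 says that a model similar to the one in 8.2.3 "will be used for analysis of the change and percent change from Erythema baseline", while 8.3 lists erythema with own baseline.
- **Scaling:** 8.2.5 says "The analysis of Scaling will be performed similar to those of erythema score as indicated in" Section 8.2.3, although erythema is in 8.2.4. Section 8.3 lists scaling too.
- **Scalpdex:** 8.3 refers to Section 8.2.2 for the ANCOVA, and 8.2.2 contains none.

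**The concern.** One analysis has two written models, and they differ in the covariate that usually matters most for a change score. If 8.2.3 is run as written, raw change is analysed without a baseline value that the trial already collects. Precision is then lost, and a chance imbalance in baseline itch passes into the estimate. The two models can give different estimates, intervals and nominal p-values.

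The results have been unblinded and presented (SAP 1). A reader who finds one set of ANCOVA results in the study report cannot tell from the SAP whether that model was the prespecified one.

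**Working it through.** The plan gives no figure on this point to reproduce. The check has three parts.

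**1. Is it the same analysis?**

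| | SAP 8.2.3 | SAP 8.3 |
|---|---|---|
| Endpoint | change and % change, average weekly WI-NRS | same |
| Visits | Weeks 2, 4, 8 | same |
| Population, data | ITT, observed | same |
| Treatment, pooled site, baseline IGA | yes | yes |
| Own baseline | not listed | listed |

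The two sections differ only in the own-baseline term.

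**2. Does anything decide between them?**

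- Protocol 6.3.2 and the synopsis give ANCOVA with treatment and the stratification factors. This matches 8.2.3. However, all eight secondary endpoints in Protocol 3.2.2 are responder endpoints, so it is unclear that the sentence reaches this one.
- SAP 6.1.2 names pooled site and baseline IGA. This also matches 8.2.3, but it says that the covariates *include* these, so it does not exclude others.
- SAP 2.2.1.3 classes the endpoint as other secondary, which is the class that 8.3 covers. This points to 8.3.
- SAP Sections 10 and 12 are silent.
- SAP 14.1 plans one ANCOVA table for average weekly WI-NRS (14.2.2.6), and its title names no covariates.

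The evidence points both ways and none of it settles the choice.

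**3. How much could it matter for raw change?**

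The documents give no SDs or correlations, so all of those below are assumptions. Let s0 be the baseline SD, s1 the follow-up SD, and r the within-arm correlation after site and baseline IGA.

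- Residual variance without own baseline: s0² + s1² − 2·r·s0·s1
- Residual variance with own baseline: s1²·(1 − r²)
- SE ratio: square root of the first divided by the second
- Shift from a baseline imbalance d: (1 − r·s1/s0)·d

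The SE of the baseline difference, with s0 = 2 and the planned 300 and 150 subjects, is 2·√(1/300 + 1/150) = 2·√0.01 = 0.20 points. If 10% or 20% lack observed data (270/135 or 240/120), it is 0.21 or 0.22. The shifts below use d = 0.20.

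Worked case, s0 = s1 = 2 and r = 0.5: variances are 4 + 4 − 4 = 4 and 4 × 0.75 = 3, the ratio is 1.333 and the SE ratio 1.155. The shift is (1 − 0.5) × 0.20 = 0.10.

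| s1 | r | Variance ratio | SE ratio | Shift (points) |
|---|---|---|---|---|
| 1.5 | 0.3 | 2.173 | 1.474 | 0.155 |
| 1.5 | 0.5 | 1.926 | 1.388 | 0.125 |
| 1.5 | 0.7 | 1.786 | 1.337 | 0.095 |
| 2 | 0.3 | 1.538 | 1.240 | 0.140 |
| 2 | 0.5 | 1.333 | 1.155 | 0.100 |
| 2 | 0.7 | 1.176 | 1.085 | 0.060 |
| 2.5 | 0.3 | 1.275 | 1.129 | 0.125 |
| 2.5 | 0.5 | 1.120 | 1.058 | 0.075 |
| 2.5 | 0.7 | 1.020 | 1.010 | 0.025 |

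For erythema and scaling, inclusion criterion 6 restricts baseline to 2 or 3, so the SD is at most about 0.5 (an even split). At s0 = 0.5, s1 = 0.7 to 0.9 and r = 0.3 to 0.7, the SE is 0% to 9% larger without own baseline. That range does not cover a less even split. With 10% severe, s0 = √(0.1 × 0.9) = 0.3; at s1 = 0.9 and r = 0.7 the variance ratio is (0.09 + 0.81 − 0.378)/(0.81 × 0.51) = 0.522/0.4131 = 1.264, which is about 12% on the SE. Percent change is not quantified.

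**The case against.** The strongest reply is that 8.2.3 is no oversight: it agrees with the only general covariate statements in either document, Protocol 6.3.2 and SAP 6.1.2. On that view the protocol-consistent model is already stated, and preferring 8.3 is a reviewer's choice on precision grounds. Part of this stands. The documents do not require 8.3, and adopting it adds a covariate to the protocol's wording, which should be recorded. It does not remove the conflict, because 8.3 states its own list for the same endpoint and neither general statement clearly governs.

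Two further replies also stand in part. Table shells are in a separate document (SAP 15.1) and may name the model, so the gap is shown only for the public text. And the effect is small: a shift of 0.03 to 0.16 points compares with a responder threshold of 4 points on a 0 to 10 scale.

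A reader might infer that the own-baseline term was chosen after unblinding. The documents do not support that. The stated purpose of SAP V3.0 is the estimand and imputation (SAP 10.2). The protocol's ANCOVA wording, in the amendment dated 05-May-2022, precedes unblinding on 19-May-2022. What the public text leaves undated is when the 8.3 term was written.

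A reader might also infer that every continuous endpoint is in conflict. Only average weekly WI-NRS has two explicit lists. For daily WI-NRS, erythema and scaling, *similar* could mean adapted to the endpoint. BSA and DLQI/CDLQI have only the 8.3 model. The scaling and Scalpdex references are section-number slips.

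**Conclusion.** The contradiction is real and the public documents do not resolve it. Severity is minor.

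If 8.2.3 is the model run, the SE for raw change in average weekly WI-NRS is about 8% to 24% larger at equal SDs and r from 0.7 to 0.3, and 1% to 47% larger over the wider grid. A one-SE baseline imbalance moves the estimate by about 0.03 to 0.16 points. These sizes rest wholly on assumed SDs and correlations.

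It would be wrong to read this as a threat to the trial's main conclusions. SAP 8.1 keeps other secondary endpoints out of the testing strategy, and 8.2.3 calls the p-values nominal. The primary endpoint, the tested secondary endpoints and type I error control are unaffected.

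**What to change.** 1. In SAP 8.2.3, use the 8.3 covariate list: treatment, pooled site, baseline IGA and the endpoint's own baseline. Make the sections that refer to 8.2.3 follow it.
2. Correct the section number in the scaling sentence of 8.2.5 (erythema is in 8.2.4), and point the Scalpdex sentence to the 8.3 model.
3. State in the SAP or clinical study report which model was programmed and when it was fixed.
4. Record in SAP Section 12 that own baseline is added to the protocol's ANCOVA covariates.
5. If the 8.2.3 model was the one programmed before unblinding on 19-May-2022, label the switch as post-unblinding and keep the 8.2.3 output as supporting.

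The cost is SAP wording and a sentence on timing. No new data are needed. If the 8.3 model was programmed, nothing is rerun; otherwise the affected ANCOVA outputs are rerun on existing data.
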